In the dose escalation phase (Cohorts 1 through 5 only) and the dose expansion phase, in Cycle 2 and beyond, a dose can be delayed up to 7 days based on hematologic and nonhematologic toxicities, according to the conditions described in Section 3.5.5, but all 3 doses (Cohorts 1 through 5 and the dose expansion phase) must be completed within the cycle in order for the cycle to be considered complete. Subjects who do not receive all required doses within a cycle will not advance to the next cycle and will be removed from treatment. Each new cycle will begin 7 days after the last dose of the previous cycle (Cohorts 1 through 5 and the dose expansion phase). Subjects in Cohorts 6 and 7 cannot have a delay in treatment due to hematologic or nonhematologic toxicities. For Cohorts 1 through 5 and the expansion phase, all visits during Cycle 2 and subsequent visits may occur in a ± 2 -day window to accommodate schedule changes, but doses of MEDI-573 must not occur more frequently than every 6 days. For Cohorts 6 and 7 (if applicable), all visits during Cycle 2 and subsequent visits may occur in a + 2-day window to accommodate schedule changes, but dosing of MEDI-573 must not occur more frequently than every 21 days.

Treatment with MEDI-573 will continue until unacceptable toxicity, documentation of disease progression, or other reasons for subject withdrawal. Rules for dose-escalation are described in Section 4.9. Intra-subject dose-escalation will not be allowed. Dose reduction for toxicities other than DLTs will be allowed as described in Section 3.5.5.

Table 3.5.2-1 Summary of Dose Cohorts

Dose Cohort	Number of Subjects	MEDI-573 Dose
1	3-6	[REDACTED] IV infusion once every 7 days
2	3-6	[REDACTED] infusion once every 7 days

Table 3.5.2-1 Summary of Dose Cohorts

Dose Cohort	Number of Subjects	MEDI-573 Dose
3	3-6	██████████ IV infusion once every 7 days
4	3-6	██████████ IV infusion once every 7 days
5	3-6	██████████ IV infusion once every 7 days
6	3-6	██████████ V infusion once every 21 days
7 (if applicable)	3-6	██████████ IV infusion once every 21 days
Dose-expansion	Up to 20	██████████ IV infusion once every 7 days

IV = intravenous

Note: The dose-expansion phase will evaluate PK and pharmacodynamic parameters and determine tumor response in approximately 20 subjects with advanced urothelial carcinoma (eg, bladder cancer).

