3.5.5 Dose Modifications of MEDI-573 Due to Toxicity

Dose modifications of MEDI-573 will be based on hematologic and nonhematologic toxicities that cannot be attributed to another cause such as disease progression or accident following the first cycle of treatment ([Table 3.5.5-1](#)). Both hematologic and nonhematologic toxicities will be graded according to NCI CTCAE V3.0. All DLTs must be documented as an AE on the source document.

Table 3.5.5-1 MEDI-573 Dose Modification Table

Hematologic or Nonhematologic Toxicity	Dose Modification of MEDI-573
Grade ≤ 1	None
Grade 2	
Cohorts 1 through 5 and the Expansion Phase
 
Withhold MEDI-573 for up to 7 days until resolution to Grade ≤ 1 or baseline and resume at current dose level. Grade 2 laboratory toxicities that do not have clinical significance may not require dose delay. The Medical Monitor should be consulted in the event of Grade 2 laboratory toxicities that are deemed clinically insignificant to determine if dosing may continue.
 
Discontinue MEDI-573 if MEDI-573 is withheld for > 7 days without resolution of toxicity to Grade ≤ 1 or baseline unless clearly attributable to another cause such as disease progression or accident.
 
Cohorts 6 and 7 (if applicable)
 
The Medical Monitor should be consulted in the event of Grade 2 laboratory toxicities that are deemed clinically insignificant to determine if dosing may continue.
 
Discontinue MEDI-573 if the toxicity does not return to Grade ≤ 1 or baseline prior to Day 1 of the subsequent cycle unless clearly attributable to another cause such as disease progression or accident.

Table 3.5.5-1 MEDI-573 Dose Modification Table

Hematologic or Nonhematologic Toxicity	Dose Modification of MEDI-573

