Grade 3 or 4	
First Occurrence:
 
Cohorts 1 through 5 and the Expansion Phase: Withhold MEDI-573 for up to 7 days until resolution to Grade ≤ 1 or baseline. Discontinue MEDI-573 if no clinical benefit has been documented . If MEDI-573 is withheld for > 7 days without resolution of toxicity to Grade ≤ 1 or baseline, discontinue MEDI-573 regardless of clinical benefit
 
Cohorts 6 and 7 (if applicable) Discontinue MEDI-573 if no clinical benefit has been documented and the toxicity does not resolve to Grade ≤1 or baseline by Day 1 of the subsequent cycle.
 
For all subjects who experience a Grade 3 or 4 toxicity that resolves as above, and who have achieved some degree of clinical benefit while on MEDI-573 therapy, the Food and Drug Administration (FDA) will be consulted regarding the possibility of continued administration of MEDI-573. MEDI-573 therapy should not be continued without agreement from the FDA.
 
Second Occurrence: Discontinue MEDI-573.

If Grade ≥ 3 toxicity that is at least possibly attributable to MEDI-573 is observed in a subject in the second or greater cycle, dose escalation will be temporarily suspended to review the cumulative safety data. Such an event may prompt cessation of dose escalation or modification of the dose-escalation scheme, including lowering of subsequent doses from the first cycle dose, if appropriate. Subjects may continue to receive MEDI-573 during this review and subjects may continue to be enrolled into an open cohort until a determination of necessary action, if any, is made.

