4.7 Interruption or Discontinuation of Study Dosing in Individual Subjects

An individual subject will not receive any further investigational product if any of the following occur in the subject in question:

- 1) Withdrawal of consent
- 2) Grade 2 or greater allergic reactions. Grade ≤ 3 infusion reactions that respond to medical therapy or slowing the infusion rate and are of limited duration will not necessitate dose interruption or discontinuation. Any infusion or allergic reaction that necessitates the use of systemic pressor agents will cause dose discontinuation in that subject.
- 3) Pregnancy or intent to become pregnant
- 4) DLT (see Section 4.10 for definition of DLTs, dose escalation phase only).
- 5) Occurrence of Grade 3 or Grade 4 hematologic or non-hematologic toxicity after the first cycle of treatment
- 6) Grade ≥ 2 toxicities (after completion of Cycle 1) that do not return to Grade ≤ 1 or baseline within 7 days unless clearly attributable to other causes such as disease progression or accident.
- 7) Grade ≥ 2 toxicities that cause a cumulative delay of ≥ 21 days in 3 consecutive cycles (Cohorts 1 through 5 and the expansion phase)
- 8) Documentation of disease progression

- 9) Event which in the opinion of the investigator contraindicates further dosing such as intercurrent illnesses, significant drug toxicities or complications if judged by the investigator to be in the best interest of the subject
- 10) Subject non-compliance
- 11) Treatment with another investigational agent
- 12) Initiation of alternative anticancer therapy

Subjects who are permanently discontinued from investigational product will be followed for the full study period (through 30 days after the last dose of MEDI-573), including the collection of any protocol-specified blood and urine specimens, unless consent is withdrawn.

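### Section 4.7 item 5 ends MEDI-573 at any Grade 3-4 toxicity after Cycle 1, but Table 3.5.5-1 lets a resolved first event in a benefiting subject continue with FDA agreement; nothing says which rule governs

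*Protocol*

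**What the plan says.** **Section 4.7.** The list names events after which a subject receives no more investigational product. Item 5 reads "Occurrence of Grade 3 or Grade 4 hematologic or non-hematologic toxicity after the first cycle of treatment". It sets no condition on resolution, benefit or FDA agreement. Item 2 spares certain infusion reactions up to Grade 3: those that respond to treatment or to a slower infusion and "are of limited duration will not necessitate dose interruption or discontinuation". Item 6 stops toxicities of Grade 2 or higher after Cycle 1 that have not returned to Grade 1 or less, or to baseline, within 7 days, unless another cause is clear. It does not distinguish cohorts.

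**Section 3.5.5, Table 3.5.5-1, Grade 3 or 4.** The table applies after the first cycle to toxicities not attributable to another cause. At a first occurrence:

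- Cohorts 1-5 and expansion: withhold for up to 7 days. Stop if there is no documented benefit, or if the toxicity has not resolved in that time.
- Cohorts 6-7: stop if "no clinical benefit has been documented and the toxicity does not resolve" by Day 1 of the next cycle.
- All subjects whose event resolves and who have benefited: "the Food and Drug Administration (FDA) will be consulted regarding the possibility of continued administration of MEDI-573". The row adds "MEDI-573 therapy should not be continued without agreement from the FDA".

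For a repeat event the table says "Second Occurrence: Discontinue MEDI-573".

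**Grade 2 row, Cohorts 6-7.** "Discontinue MEDI-573 if the toxicity does not return to Grade ≤ 1 or baseline prior to Day 1 of the subsequent cycle", again with an other-cause exception. Section 3.5.2 adds: "Subjects in Cohorts 6 and 7 cannot have a delay in treatment due to hematologic or nonhematologic toxicities".

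**The concern.** The two sections give opposite final answers for the same subject: a first Grade 3-4 event after Cycle 1 that has resolved, in someone who is benefiting, with FDA agreement. If item 5 governs, the FDA route and the separate second-occurrence stop can never operate. If the table governs, item 5 is too broad.

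The practical risk is that a benefiting subject is taken off drug without the consultation that the table calls for, or that two sites handle the same case differently. A subject stopped without progression also moves from disease evaluation every 2 cycles (6 weeks) to every 3 months (Sections 2.4 and 3.6), so a later progression is dated more coarsely.

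**Working it through.** The main check is a comparison of texts. The Protocol gives no figure to reproduce.

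**Step 1: the four branches.** Take a first Grade 3-4 event after Cycle 1 that is not attributable to another cause and is not an exempt infusion reaction. *Resolved* means to Grade 1 or less, or baseline, within 7 days (Cohorts 1-5 and expansion) or by Day 1 of the next cycle (Cohorts 6-7).

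| Benefit | Resolved | Item 5 | Table, Cohorts 1-5 and expansion | Table, Cohorts 6-7 |
|---|---|---|---|---|
| No | No | Stop | Stop | Stop |
| No | Yes | Stop | Stop | No order |
| Yes | No | Stop | Stop | No order |
| Yes | Yes | Stop | Continue if FDA agrees | Continue if FDA agrees |

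Item 5 and the table expressly conflict in 1 of 4 branches, the last, in every cohort. In Cohorts 6-7 the table is silent in 2 of 4.

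**Step 2: is precedence stated?** The Study Abstract and Section 2.4 point to Section 4.7 for interruption and discontinuation, and to Section 3.5.5 for dose reduction. Section 3.5.2 points to Section 3.5.5 for delays. These say where rules are found; none ranks them, and the table itself orders discontinuation. Item 5 does not refer to the table.

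**Step 3: what fills the silent branches in Cohorts 6-7?** Item 5 stops the drug in both. Within the table, FDA consultation is offered only after resolution with benefit, and the row bars continuing without FDA agreement. Item 6 adds a stop once 7 days have passed without resolution. No text orders or permits redosing in either branch. The defect is that the Grade 3-4 row, read alone, requires both conditions for a stop, whereas the Grade 2 row stops on non-resolution alone.

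**Step 4: item 6 against the table in Cohorts 6-7.** Let onset be on cycle Day d (1 to 21), ignoring the +2-day visit window.

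- Item 6 limit: Day d + 7.
- Table limit: Day 22, which is Day 1 of the next cycle.
- The limits are equal when d + 7 = 22, so d = 15.
- For d = 1 to 14, item 6 is earlier: 7 days against 22 - d days, up to 21.
- For d = 16 to 21, the table is earlier.

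Example: a Grade 2 event starts on Day 3 and resolves on Day 15. It lasted 12 days, so item 6 stops the subject. It resolved before Day 22, so the table does not.

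**Step 5: how often?** Section 1.5 reports 17 subjects treated to 17 February 2010, with treatment-related events of Grade 1 or 2 only. That is 0 of 17 with a treatment-related Grade 3-4 event. The exact two-sided 95% upper limit is 1 - 0.025^(1/17) = 1 - 0.805 = 0.195, or about 19.5%. The conflicting branch is narrower still, because it also needs onset after Cycle 1, resolution, benefit and FDA agreement.

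**The case against.** The strongest reply is that Section 4.7 is meant to control. The cross-references send the reader there for discontinuation, and Appendix 4 records that item 5 was changed from *Recurrence* to *Occurrence*, which looks deliberate. This stands as evidence of intent and favours the stricter rule. It does not settle the matter: the current table, revised again later for Cohorts 6-7, still carries the FDA route and the second-occurrence stop. A reader might infer that item 5 is simply a mistake to be loosened. The documents do not support that.

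A second reply is that no site can redose on its own authority. This also stands: until the FDA agrees, both texts give no drug. In addition, a Grade 3 or higher event at least possibly due to drug in Cycle 2 or later suspends escalation for a safety review, so the sponsor will see it while escalation is open. Appendix 4 also describes Cohorts 6-7 as limited to one centre, which leaves little room for differences between sites there.

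A reader might infer from the *and* that subjects in Cohorts 6-7 with unresolved Grade 3-4 toxicity may be redosed if they are benefiting. That would be a safety hazard, but the documents do not support it: the table is merely silent, and item 5 and the FDA-agreement sentence block dosing, as does item 6 once its 7 days have run. Nor does item 5's lack of an other-cause exception, which item 6 has, amount to a contradiction. It is a difference in scope.

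**Conclusion.** The inconsistency is real and should be fixed. It is confined to one of the four benefit-by-resolution branches, in every cohort, and there the two rules cannot both be obeyed. The *and* in the Cohorts 6-7 row and the unrestricted 7 days in item 6 are genuine but secondary.

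The likely number of subjects is small. That rests on the early experience in Section 1.5, which covers weekly dosing only, stops at the cutoff, and uses treatment-relatedness as a stand-in for the table's criterion of no other cause. It does not exclude later events or events in Cohorts 6-7. DLTs are assessed in Cycle 1 only, so dose escalation, the MTD and the sample size are unaffected. What is at stake is whether an individual benefiting subject is considered for continued dosing.

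**What to change.** The sponsor states which rule governs and amends accordingly.

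- **Option A, item 5 governs (the stricter rule).** Replace the whole Grade 3-4 row of Table 3.5.5-1 with *Discontinue MEDI-573* for all cohorts, and keep the infusion-reaction exemption in item 2.
- **Option B, the table governs.** Add to item 5: *except where continuation is permitted under Table 3.5.5-1 (first occurrence, resolved to Grade 1 or less or baseline, documented clinical benefit, FDA agreement)*. In the Cohorts 6-7 Grade 3-4 row, change *and* to *or*.

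Under either option, limit the 7 days in item 6 to Cohorts 1-5 and expansion, and use Day 1 of the next cycle for Cohorts 6-7.

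The cost is amendment wording only: item 6 plus one table row (A), or items 5 and 6 plus one word in the table (B). No assessment, sample size or analysis changes.

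### After Cycle 1, Section 4.7 item 6 stops Grade 2 toxicities at 7 days in every cohort, while Table 3.5.5-1 gives Cohorts 6 and 7 until the next Day 1 and provides a laboratory route that item 6 lacks

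*Protocol*

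**What the plan says.** Both passages are current text, and both govern the period after Cycle 1.

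- **Protocol Section 4.7, opening line.** "An individual subject will not receive any further investigational product if any of the following occur in the subject in question". Meeting any one item is enough to end dosing.
- **Section 4.7 item 6.** "Grade ≥ 2 toxicities (after completion of Cycle 1) that do not return to Grade ≤ 1 or baseline within 7 days", with an exemption for toxicities clearly due to another cause; the limit and its exemption read "or baseline within 7 days unless clearly attributable to other causes such as disease progression or accident". It names no cohort and has no laboratory exception.
- **Section 4.7 item 7, directly below.** This one is limited by cohort: "cumulative delay of ≥ 21 days in 3 consecutive cycles (Cohorts 1 through 5 and the expansion phase".
- **Section 4.7 item 5.** Grade 3 or 4 toxicity after Cycle 1 ends dosing when it occurs.
- **Table 3.5.5-1 (Section 3.5.5), Grade 2, Cohorts 6 and 7.** "Discontinue MEDI-573 if the toxicity does not return to Grade ≤ 1 or baseline prior to Day 1 of the subsequent cycle", with a similar exemption for other causes.
- **Table 3.5.5-1, Grade 2, Cohorts 1 through 5 and expansion.** "Grade 2 laboratory toxicities that do not have clinical significance may not require dose delay".
- **Table 3.5.5-1, Grade 2, both cohort groups.** The Medical Monitor is to be consulted on clinically insignificant Grade 2 laboratory toxicities, to settle whether dosing may go on.

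No sentence in the protocol says which passage prevails.

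**The concern.** Section 4.7 restricts items to particular cohorts or phases where it means to (items 4 and 7). Item 6 carries no restriction, so as written its 7-day limit binds Cohorts 6 and 7. The table sets those cohorts a different deadline for the same toxicity grade over the same period. A site working from the table can keep a subject on drug whom Section 4.7 requires it to stop.

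The laboratory provision raises the same problem in a different form. The table gives the Medical Monitor a decision to make, and item 6 leaves no room for that decision once 7 days have passed.

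At stake is who stays on treatment, and so the number of cycles received, the later-cycle PK and biomarker samples tied to dosing days (Sections 3.7.5 and 3.7.6.1), and the discontinuation summaries. Cohorts 6 and 7 have 3 to 6 subjects each (Table 3.5.2-1), so one stop is visible in a cohort summary. Cohort 6 data on PK, pharmacodynamics, immunogenicity and safety also inform the decision on Cohort 7 (Section 5.1).

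As context only, Appendix 4 records that the amendment introducing the current Cohorts 6 and 7 revised the table for them, but for Section 4.7 it lists only a DLT clarification. That would fit an item carried over without being harmonised.

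**Working it through.** The plan gives no figure to reproduce. The check is a comparison of the two rules and a day count.

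**Inputs**
- Item 6 limit: 7 days, all cohorts, after Cycle 1 (Section 4.7).
- Table limit for Grade 2 in Cohorts 6 and 7: before Day 1 of the next cycle (Table 3.5.5-1).
- Cycle length in Cohorts 6 and 7: 21 days, no earlier redosing, visit window of + 2 days, no toxicity delays (Section 3.5.2).

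**Which grades matter.** Item 5 already stops Grade 3 and 4 after Cycle 1, so item 6 makes a difference of its own only for Grade 2.

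**Time allowed by the table.** A toxicity with onset on Day d has 22 − d days until the next Day 1.

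| Onset | Table allows | Item 6 allows |
|---|---|---|
| Day 1 | 22 − 1 = 21 days | 7 days |
| Day 14 | 22 − 14 = 8 days | 7 days |
| Day 15 | 22 − 15 = 7 days | 7 days |
| Days 16 to 21 | 6 down to 1 day | 7 days |

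For onset on about Days 1 to 14 the table is the more permissive rule. If the next dose is given at the end of the + 2-day window, the time allowed is 24 − d and the table is more permissive for Days 1 to 16.

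**Example.** A Grade 2 event in Cohort 6 begins on Day 3 of Cycle 2 and resolves on Day 14, so it lasts 14 − 3 = 11 days. Item 6 is met once Day 3 + 7 = Day 10 passes unresolved, and the subject must stop. Under the table the event clears before Day 22, the next Day 1, so the stop is not met.

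**Illustrative share.** Assume onset is uniform over 21 days and the event lasts a fixed D days, with 7 < D < 21. Item 6 always stops such an event. The table does not stop it if onset + D ≤ 21, which has probability (21 − D)/21:
- D = 8: 13/21 = 62%
- D = 10: 11/21 = 52%
- D = 14: 7/21 = 33%

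With the next dose at the end of the + 2-day window the numerator is 23 − D, giving 15/21 = 71%, 13/21 = 62% and 9/21 = 43%.

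**Laboratory values.** In Cohorts 1 through 5 and expansion, the table's Grade 2 stop is triggered by withholding drug for more than 7 days without resolution. If a value judged insignificant leads to no withholding, that stop is never triggered, yet item 6 is met once the value has persisted beyond 7 days. In Cohorts 6 and 7 the table provides the consultation, but the discontinuation sentence that follows has no laboratory exception. There, the gap is between the Medical Monitor's decision within the cycle and item 6's 7-day limit.

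**The case against.** The strongest reply is that Section 4.7 is a list of sufficient reasons to stop, and that the Cohorts 6 and 7 cell only says when to discontinue. It does not tell the site to resume dosing, as the cell for Cohorts 1 through 5 does. A site could obey both by stopping as soon as either condition is met. That is right, and it limits the point. On that reading, however, the separate Cohorts 6 and 7 deadline would have no effect for early onsets, and the Medical Monitor's decision would be void after 7 days. Nothing in the protocol tells a site to read it that way. Section 2.4 refers readers to Section 4.7 for discontinuation and to Section 3.5.5 for dose reduction, which helps but does not set an order of precedence.

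The same reply disposes of a stronger reading. A reader might infer that the rules conflict in both directions, because an event from Day 18 to Day 24 lasts under 7 days yet is unresolved at the next Day 1. Section 4.7 never says such a subject continues. Item 6 is silent, the table adds a stop, and both can be followed. Shares computed for events of 7 days or less would rest on this reading and are not claimed.

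Further limits stand:
- The table does not let insignificant laboratory values continue automatically. The Medical Monitor is consulted, and the sentence on not needing a delay appears only for Cohorts 1 through 5 and expansion.
- That the table's allowance depends on when in the cycle a toxicity begins is a feature of a clinical rule, not a contradiction.
- From Cycle 2, Cohorts 6 and 7 have scheduled visits only on Days 1 and 8 and every 2 cycles (Table 3.6-2), so exact onset and resolution of a laboratory toxicity would often not be observed.

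**Conclusion.** The inconsistency holds in one direction. After Cycle 1, a Grade 2 toxicity in Cohorts 6 or 7 that starts on about Days 1 to 14, lasts more than 7 days, clears before the next Day 1 and is not clearly due to another cause must end treatment under Section 4.7 item 6 but not under Table 3.5.5-1. In addition, item 6 has no counterpart to the table's Grade 2 laboratory provision, in the form that provision takes for each cohort group.

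The 62%, 52% and 33% rest on uniform onset and chosen durations. The protocol gives no data on either, so they show that the gap is not confined to rare timings and say nothing about how often it will occur. The deadline mismatch reaches two small cohorts, one of which may not open.

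A reader might infer that the dose-finding result or the progression endpoints are undermined. The documents do not support that. DLTs are assessed only in Cycle 1 (Section 4.10), so the MTD evaluation is untouched. Subjects who stop for toxicity keep having disease evaluations every 3 months (Section 2.4), so follow-up for progression does not end with dosing. What is affected is time on treatment, later-cycle exposure and samples, and the discontinuation summaries.

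**What to change.** Reconcile Section 4.7 item 6 with Table 3.5.5-1 on three matters:

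1. **Cohort scope:** state which cohorts item 6 covers, as item 7 does.
2. **Resolution deadline:** give one Grade 2 deadline for Cohorts 6 and 7 in both places.
3. **Laboratory values:** make the two passages agree on clinically insignificant Grade 2 laboratory toxicities and on the Medical Monitor's role, for each cohort group.

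Alternatively, add a sentence saying which passage prevails. The clinical team decides which limit applies; this review takes no position on it. The cost is amendment wording, with no change to sample size or analysis methods.
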